### 2.5.2 Reference drug formulations

THN102 Placebo is a combination drug constituted by modafinil 100 mg placebo tablets over-encapsulated and by flecainide placebo capsules. Daily dosages are: Modafinil 0 mg and flecainide: 0 mg.

**Drug code:** Modafinil placebo  
**Dosage form:** 1 tablet of 0 mg, over-encapsulated (orange capsule)  
**Excipients:** Tablet: Lactose monohydrate, pregelatinised starch (maize), microcrystalline cellulose, croscarmellose sodium, Povidone K29/32, magnesium stearate.  
Capsule, filler: Gelatine, Swedish Orange, microcrystalline cellulose.  
**Vials:** Capsules will be provided into HDPE snap-cap vials containing 18 capsules each.  
**Storage:** 15-25 °C (avoid exposure >25°C)  
**Route:** Oral  
**Dose:** 2 capsules containing 0 mg each, at 8:00 h (± 1:00 h) in the morning  
A 24-hour (± 1:00 h) interval between two consecutive doses is required.

For subjects aged above 65 years:  
On the first, second and third day of each treatment period, 1 capsule will be taken.  
From the fourth to the last day of each treatment period, the regimen will be as described above.

**Drug code: Flecainide placebo**

Dosage form: 0 mg of flecainide powder per capsule (white capsule)

Excipients: Tablet: Microcrystalline cellulose (Avicel PH112), magnesium stearate.  
Capsules: Hypromellose (HPMC)

Storage: 15-25 °C

Route: Oral

Vial: Capsules will be provided in HDPE snap-cap vials containing 18 capsules each.

Dose: 2 capsules containing 0 mg each, in the morning at the same time as modafinil placebo.

For subjects aged above 65 years:  
On the first, second and third day of each treatment period, 1 capsule will be taken.  
From the fourth to the last day of each treatment period, the regimen will be as described above.

## 2.6 Sample Size

For sample size planning ESS was considered to be the key efficacy endpoint. Solid information on the expected difference between placebo and THN102 dose and the associated intrasubject variance were not available. Using results reported in Adler et al. [4] as a rough orientation an effect size of 0.40 may constitute a conservative estimation for the comparison of the high THN102 dose with placebo. A sample size of 54 subjects will have a power of 82% to detect this effect size based on a paired t-test with a 0.05 two-sided significance level. To account for drop outs 60 subjects will be randomised.

In this exploratory phase 2a study, no adjustment for multiple testing will be applied.

## 2.7 Blinding

Modafinil 100 mg capsules and modafinil placebo capsules are identical in size, colour and appearance. The packaging and labelling will not allow for any distinction between them.

Likewise, flecainide 1 mg capsules, flecainide 9 mg capsules and flecainide placebo capsules are identical in size, colour and appearance. The packaging and labelling will not allow for any distinction between them.

During the trial, the subject and all personnel involved with the conduct and the interpretation of the trial, including the investigators, site personnel, and the sponsor's staff, are blinded to the treatment assignment. The randomisation schedule is filed securely by the clinical CRO, in a manner such that blinding is properly maintained throughout the trial. Treatment assignment will not be available until the completion of the trial and until after final data review (clinical data base lock), except in the case of emergency.

## 3. ANALYSIS SETS AND SUBGROUPS

### 3.1 Analysis sets

The **Enrolled Set (ES)** includes all subjects who have signed the informed consent form.

The **Randomised Set (RS)** includes all subjects randomised at visit VR.

The **Safety Set (SS)** includes all subjects with at least one IMP administration.

The **Full Analysis Set** (FAS) includes all randomised subjects with an evaluable ESS score at the end of at least one treatment period. Evaluability of treatment periods is described in Section 5.6. The efficacy analyses will be conducted on the FAS.

The **Per Protocol** (PP) set includes all subjects in the FAS who have at least one treatment period without a major protocol deviation. Major and minor violations are defined in Sections 5.1.2 and 5.6. The main secondary endpoints (ESS, PVT and cognition) will be analysed with the PP set to demonstrate robustness of the primary analysis.

The **PK analysis set** will include all subjects who have received treatment as per protocol (even if the trial was not completed) and who present no major protocol deviations with an impact on PK.

### **3.2 Subgroups**

No subgroups are defined for the primary analysis of this study.

## 4. GENERAL DEFINITIONS AND NAMING CONVENTIONS

To avoid ambiguity during the analysis, a number of definitions and conventions for data handling are described here.

### 4.1 General Methodology and Presentation of the Results

The default summary statistics for quantitative (continuous) variables will be

- the number of subjects (n),
- mean,
- standard deviation (SD),
- median,
- first quartile (Q1) and third quartile (Q3)
- minimum (min) and maximum (max)

for subjects with data. Additionally, the geometric mean (GeoMean), geometric standard deviation (GSD), and geometric coefficient of variation (GCV) will be displayed for certain variables. Values of '0' will be removed from the calculation of the geometric mean, GSD, and GCV.

Mean, geometric mean, median, and the quartiles will be presented to one more decimal place than the raw value. The minimum and maximum values will be presented with the same decimal precision as the raw value. SD, GSD, and GCV will be reported to two decimal places greater than the original value.

For qualitative (categorical) variables, the frequency count (n) and percentage (%) of subjects with non-missing data per category will be the default frequency tabulations. Where appropriate and present, the number of missing values will be displayed as "Missing" category.

Percentage values are to be presented to one decimal place, for example, 52.3%.

The denominator used for calculation of the percentages will be specified in a footnote to the tables for clarification.

### 4.2 Statistical Output Layout

All titles and column headers (consisting of one or several words) will be capitalised; articles, prepositions, and conjunctions, and "To" in infinitives will not be capitalised, except they are at the beginning of titles or headers.

All pages will be numbered according to the table/listing/figure to which the page belongs to. Every table/listing/figure will be numbered from page 1, "Page X of Y" at the bottom of each page.

The definition of baseline and endpoint value will be described in a footnote in every TLF where applicable. Other important definitions will also be presented if necessary.

Dates will be listed in the format: yyyy-mm-dd (e.g. 2003-11-20). Times will be listed in the format: hh:mm (e.g. 09:15) or in the format hh:mm:ss if seconds are collected. When the date and time are collected, these are listed in the format: yyyy-mm-ddThh:mm (e.g. 2003-11-20T09:15), yyyy-mm-ddThh, or yyyy-mm-ddThh:mm:ss.

Partially missing dates will be listed in the format yyyy-mm (e.g. 2013-11) if only day is missing or in the format yyyy (e.g. 2013) if month and day are missing.

Missing data including missing dates or times will be displayed in listings as blank fields, unless otherwise specified.

Listings will be sorted by subject's number and visit number where applicable, unless specified otherwise.

### 4.3 Treatment Group Names and Labels

Statistical output will be presented by treatment sequence or treatment. Tables and figures that are displayed by treatment sequence or by treatment will be labelled with an S or T respectively. The labels used for treatment sequences and pooled treatment groups can be seen below (Table 3 and Table 4 respectively). For more details data pooling by treatment, see Sections 4.6-4.8.

**Table 3: Sequence Labels**

Description	Label in Statistical Output
Sequence 1: Dose A – Dose B – Dose C	ABC
Sequence 2: Dose B – Dose C – Dose A	BCA
Sequence 3: Dose C – Dose A – Dose B	CAB
Sequence 4: Dose A – Dose C – Dose B	ACB
Sequence 5: Dose C – Dose B – Dose A	CBA
Sequence 6: Dose B – Dose A – Dose C	BAC

**Table 4: Treatment Labels**

Description	Label in Statistical Output
Placebo	Placebo or A
THN102 200 mg/2 mg	Test 200/2 or B
THN102 200 mg/18 mg	Test 200/18 or C

### 4.4 Visit Numbering and Labels

The numbers to be used in the analysis datasets and the labels to be used in the tables, listings and figures for the different trial visits are defined in Table 5.

**Table 5: Visit Numbering and Labels**

Visit number	Visit name	Label in Statistical Output
10	Screening – VS1	VS1
20	Actigraphy – VS2	VS2
30	Baseline – VR	VR
40	Actigraphy – V1A	V1A
50	End of treatment I – V1B	V1B
60	End of washout I – V1C	V1C
70	Actigraphy – V2A	V2A
80	End of treatment II – V2B	V2B
90	End of washout II – V2C	V2C
100	Actigraphy – V3A	V3A
110	End of treatment III – V3B	V3B
120	Early Discontinuation Visit – EDV	EDV
130	Follow-up – V3C	V3C

The values collected at the EDV will be slotted according to date of EDV occurrence (see Section 4.6).

#### 4.5 Treatment Day Numbering

All assessment dates will be related to the first day of IMP intake during the first treatment period. This first day of IMP intake is referred to as Day 1. Day -1 is the day that is preceding Day 1 and Day 0 will not be defined.

Treatment days may alternatively be numbered in listings with reference to the ongoing treatment period using the following rules:

- Dates prior to or during the first treatment period will be numbered with reference to the date of first IMP intake as described above.
- Dates belonging to the second and third treatment periods will be numbered with reference to the day after visit V1C or V2C respectively.
- Treatment days during any treatment period will be labelled according to the planned treatment sequence of the subject (e.g. A-11 for day 11 of the first treatment period in the sequence ABC). Treatment days prior up to visit VR will be labelled without reference to treatment sequence.

#### 4.6 Trial Periods

##### Baseline period

The baseline period will be defined as the period from informed consent signature date to the date of visit VR.

##### Treatment periods

The periods from the day after visits VR, V1C, and V2C, to the dates of visits V1B, V2B, and V3B respectively, will be defined as the three treatment periods of this trial.

Data collected at visits V1B, V2B, and V3B will be considered as end-of-treatment values for their respective treatment periods.

If an early discontinuation visit (EDV) occurs after 7 or more IMP intakes, and not more than 3 days after the last IMP intake, the data collected at the EDV will be assigned to the end of the ongoing treatment period for statistical analyses.

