##### Washout periods

The periods from the day after visits V1B and V2B, to the dates of visits V1C and V2C respectively will be defined as the two washout periods of this trial.

Data collected at visits V1C and V2C will be considered as end-of-washout values for the first and second treatment periods respectively and will be summarised within the same treatment as the end-of-treatment values of the respective treatment period.

If an EDV occurs 6 or more days after the last IMP intake of the preceding treatment period, the data collected at the EDV will be assigned to the end of the ongoing washout period for statistical analyses.

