## 4.8 Treatment Assignment

In summaries and analyses where data is pooled by treatment, assignment to treatments will be performed as follows:

- Data collected up to and including visit VR (baseline) will be assigned to all treatments.
- Data collected at visits V1A-V1C, V2A-V2C, V3A-V3B, will be assigned to the treatment corresponding to the first, second and third treatment period respectively
- Data collected at the EDV visit will be assigned to treatment periods according to the rules in Section 4.6
- Efficacy analyses will be performed according to treatment **as randomised**. Data will be assigned to treatments based on the combination of planned treatment sequence and treatment period.
- Safety analyses will be performed according to treatment **as treated**. Data will be assigned to treatments based on the treatment actually received during the corresponding treatment period.

Other features of or deviations from the rules of treatment assignment are discussed in the relevant sub-sections of Section 5.

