### 5.3 Prior and Concomitant Medications

Prior and concomitant medications and therapies are documented in the eCRF.

The following information is collected:

- Medication / therapy name
- Indication (Parkinson's disease, excessive daytime sleepiness, medical history diagnosis – specified, adverse event – specified, other)
- Route
- Total daily dose (units)
- Frequency
- Start date
- Stop date (or ongoing)

Medications and therapies will be classified as 'prior', 'concomitant' or 'post-treatment' based on start/stop dates:

- **Prior medications/therapies** are defined as those medications/therapies starting and ending prior to the first IMP intake as recorded in the eCRF.
- **Concomitant medications/therapies** are defined as medications/therapies started at or after the first IMP intake as recorded in the eCRF and include medications/therapies started prior to the first IMP intake but continued during the trial.
- **Post-treatment medications/therapies** are defined as medications/therapies which started after the last IMP intake as recorded in the eCRF.

If the start date of medication/therapy is incomplete or missing, it will be assumed to be concomitant except if the incomplete start date or the stop date indicates that the medication/therapy started prior to the first IMP intake or after the last IMP intake.

Concomitant medications will be assigned to treatments based on the preceding IMP intake. Medications taken during a washout period will be assigned to the treatment of the IMP taken in the preceding treatment period. If the start or end date indicates that the medication was taken concurrently with multiple treatments, it will be assigned to every corresponding treatment. If the start or end date is incomplete such that it could belong to more than one treatment, the concomitant medication will be assigned to all such treatments.

The following tables and listings will be provided:

Table 15.1.9.1.1.S Prior Medications – Safety

Table 15.1.9.1.2.S Prior Medications – Full Analysis

Table 15.1.9.2.1.T Concomitant Medications – Safety

Table 15.1.9.2.2.T Concomitant Medications – Full Analysis

The number and percentage of subjects with at least one medication within each ATC 2nd level subgroup and substance name will be presented for the respective set. The ATC 2nd level subgroups and substance name within ATC 2nd level subgroup will be ordered by descending overall incidence.

Listing 16.2.4.4 Medications and Therapies – Enrolled

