### 5.5.1 Adverse Events

AEs will be coded according to MedDRA Version 21.0.

Adverse event data includes:

- adverse event name
- start date
- stop date or ongoing
- severity (mild, moderate, severe)
- relationship to the IMP (unrelated, unlikely, possible, probable, definite)
- action taken with IMP (no action, drug interrupted, drug withdrawn, unknown)
- other actions (none, medication required, tests required, hospitalisation required or prolonged, other)

- outcome (recovered/resolved, recovered/resolved with sequelae, recovering/resolving, not recovered/not resolved, fatal, unknown) and date of outcome
- serious (yes or no)

All AEs will be presented in listings.

Adverse event summaries will focus on **treatment-emergent adverse events (TEAEs)**, defined as AEs with an onset or worsening after the first IMP intake and not more than 7 days after the last IMP intake.

If the start date of an AE is incomplete or missing, it will be assumed to be treatment-emergent except if the stop date or the incomplete start date indicates that the event started prior to the first IMP intake or later than 7 days after the last IMP intake.

Treatment-emergent adverse events will be assigned to treatments based on the treatment period containing the AE onset date. If the onset date of an adverse event is during a washout period, it will be assigned to the preceding treatment period. If the AE onset date is incomplete such that it could belong to more than one treatment period, the AE will be assigned to all treatments corresponding to such treatment periods.

Based on collected data the following will be determined and will be used in addition to AEs overall for presentation in the applicable tables and listings:

- **Serious Adverse Events (SAEs):** defined as AEs considered by the investigator as serious.
- **Related TEAEs:** defined as AEs with relationships to the IMP assessed as being “possible”, “probable” or “definite” and include AEs with missing IMP relationship assessments.
- **Unrelated TEAEs:** defined as AEs with relationships to the IMP assessed as being “unlikely” or “unrelated”.
- **Severe TEAEs:** defined as AEs assessed as being “severe” in intensity and include the events with missing severity assessment.
- **TEAEs leading to discontinuation:** defined AEs whose action taken with IMP is “drug withdrawn” or other action taken is “withdrawal from trial”.

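### If the first dose of period II or III is late, SAP 5.5.1 tabulates adverse events from the undosed gap under a treatment not yet taken

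*SAP*

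**What the plan says.** Period boundaries in SAP 4.6 are visit dates. For treatment: "The periods from the day after visits VR, V1C, and V2C, to the dates of visits V1B, V2B, and V3B respectively, will be defined". For washout: "The periods from the day after visits V1B and V2B, to the dates of visits V1C and V2C respectively". One period therefore ends on the V1C or V2C date and the next opens the following day, with no reference to intake.

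SAP 5.5.1 builds on these periods: "Treatment-emergent adverse events will be assigned to treatments based on the treatment period containing the AE onset date". An onset during washout goes back to the preceding treatment period. TEAEs are "defined as AEs with an onset or worsening after the first IMP intake and not more than 7 days after the last IMP intake". SAP 5.4.1 takes the last intake from the trial termination page, so this window spans the whole trial and does not reopen in each period.

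Safety data are analysed as treated under SAP 4.8: "Data will be assigned to treatments based on the treatment actually received during the corresponding treatment period". Medications follow a dose-based rule in SAP 5.3: "Concomitant medications will be assigned to treatments based on the preceding IMP intake".

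Protocol 5.1.3 and footnote 1 of the flow chart place the first intake of each period on the day after VR, V1C or V2C. That is the day on which the SAP period opens.

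**The concern.** The SAP uses the scheduled first-dose date in place of the actual one. When the two differ in period II or III, the undosed days belong to the new treatment for adverse event tabulation. No other rule moves them:

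- The TEAE definition screens out pre-dose events only in period I. Later, earlier dosing has already made any new event emergent.
- The as-treated rule works on whole periods and does not separate days before the first dose from days after it.
- PD#27 in SAP 5.1.2 puts the duration of treatment and washout periods up for case-by-case review, but carries no rule for reassigning events.

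Safety against placebo is the primary objective, and the by-treatment TEAE tables are central to it. Gap events may also be more frequent than the number of gap days suggests, since a subject who falls ill just after V1C or V2C may delay the first dose for that reason.

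**Working it through.** The plan gives no figure to reproduce here. The check applies the rules day by day and then sizes the result.

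**Inputs.** Last period I dose and V1B on Day 14. V1C on Day 21, with a window of -1/+7 days, so Day 20 to Day 28 (flow chart). The rules of SAP 4.6 and 5.5.1. Delays in the first period II dose are assumed, because the documents give none.

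**Step 1: assignment of onsets after V1C.**

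| V1C | First dose, period II | Onset days before that dose | Days since last period I dose | SAP 5.5.1 assigns to | Most recent intake |
|---|---|---|---|---|---|
| Day 21 | Day 22 (as scheduled) | none | – | – | – |
| Day 20 | Day 22 | 21 | 7 | period II | period I |
| Day 21 | Day 24 | 22, 23 | 8, 9 | period II | period I |
| Day 28 | Day 31 | 29, 30 | 15, 16 | period II | period I |

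Misattributed days = actual first-dose day − (V1C day + 1). This is 0 for an on-time start and equals the delay otherwise. With an on-time start, only the hours before the dose (scheduled for 08:00 h ± 1 h) on that one day remain. The same holds for V2C and period III.

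**Step 2: share of observation time, under assumptions.** Suppose 5% to 10% of period II and III starts are 1 to 3 days late. Each such period has about 14 + 7 = 21 days of observation.

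- Low: 0.05 × 1 / 21 = 0.2%
- High: 0.10 × 3 / 21 = 1.4%

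Period I contributes none, so over all three periods the share is two thirds of this: about 0.16% to 0.95%. The share of events could be higher if illness causes the delay.

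**Step 3: effect of one misplaced subject.** With the 60 planned safety subjects, one subject changes a column by up to 1/60 = 1.7 percentage points. If the event leaves one column and enters another, the difference between those columns changes by up to 2/60 = 3.3 points. This holds for a given preferred term if the subject has no other such event under either treatment.

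**Step 4: direction.** Transitions in the six sequences (A = placebo, B and C = THN102):

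- ABC: A→B, B→C
- BCA: B→C, C→A
- CAB: C→A, A→B
- ACB: A→C, C→B
- CBA: C→B, B→A
- BAC: B→A, A→C

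Each of the six ordered pairs occurs twice. Of 12 transitions, 4 run from placebo to THN102, 4 from THN102 to placebo, and 4 between THN102 doses.

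**Step 5: comparison with the medication rule.** A short course taken wholly within the gap goes to the previous treatment under SAP 5.3, while the event it treated goes to the new one under 5.5.1. A course that continues past the first dose is assigned to both treatments, so the mismatch is confined to short courses.

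**The case against.** The strongest reply is that the period start in SAP 4.6 is the scheduled first-dose date. No whole day is misassigned unless a subject departs from Protocol 5.1.3, and such departures are visible: SAP 5.4.1 tabulates visit-based and intake-based durations together, and PD#27 prompts review. That limits the size. It does not remove the fault, because visibility does not move an event to another column.

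A reader might infer that the rule charges events to THN102 after a placebo period and so biases the comparison against the drug. The documents do not support this. The transitions balance as in Step 4, and under blinding the treatment about to start cannot affect events that precede it. Gap events may be non-random in time without being non-random by upcoming treatment.

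A reader might also see a breach of the as-treated principle in SAP 4.5, where "Dates belonging to the second and third treatment periods will be numbered with reference to the day after visit V1C or V2C respectively" and "Treatment days during any treatment period will be labelled according to the planned treatment sequence of the subject". That numbering is optional and for listings only. Table assignment is governed by SAP 4.8, so the label changes no table. Nor are SAP 5.3 and 5.5.1 opposite rules: within the visit-defined washout both use the preceding treatment.

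A fair further point is that the previous treatment is not clearly the right home for these events. In Step 1 they fall 7 to 16 days after its last dose, mostly beyond the 7-day limit of the TEAE definition. That stands as a cost of the fix. But the SAP already accepts it for washout: with V1C on Day 28, an onset that day is 14 days after the last dose and still goes to the preceding period.

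**Conclusion.** The point holds as a limited one. For a late first dose in period II or III, the stated rules place an event from the gap under a treatment the subject has not yet taken. Period I is not affected, and neither are onsets on or before the V1C or V2C date. With on-time dosing the only residue is an onset before the dose on the first day.

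The number of misattributed days equals the delay. The figure of 0.2% to 1.4% of observation time in periods II and III rests wholly on the assumed 5% to 10% of late starts of 1 to 3 days. The expected result is slight misclassification spread over the three columns, not a systematic shift against THN102. It deserves correction because the affected tables serve the primary objective and the remedy is cheap.

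**What to change.** Leave the period definitions in SAP 4.6 as they are. Visit, diary, washout and early-discontinuation rules depend on them, and moving the period start would stretch washout past its own end-of-washout visit.

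Change SAP 5.5.1 only:

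- Assign each TEAE in periods II and III to the treatment actually received at the most recent IMP intake on or before the onset date, using the eCRF date with the diary as fallback. Onsets after V1C or V2C but before the first intake then stay with the preceding treatment, as washout onsets already do.
- State a convention for onsets on the day of first intake. The SAP's adverse event data list only a start date, so dates alone cannot order the two. As worded above, such onsets would go to the new treatment.
- Keep the existing rule for incomplete onset dates.

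The cost is one extra derivation and no new data: SAP 5.4.1 already needs first and last intake dates within each period, and SAP 5.3 already uses the preceding intake. The drawback is that some gap events more than 7 days after the last dose will be attributed to the previous treatment. The change should be settled before unblinding.

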### Endpoint value

The endpoint value for a variable is defined as the last non-missing value collected during any end-of-treatment visit (V1B, V2B, or V3B).

For diary data, the endpoint value will be the value standardized as described in Section 5.6.8 over any treatment period corresponding to a given treatment.

**Absolute change from baseline** will be calculated as

$$\text{Absolute Change from Baseline at Visit } X = \text{Value at Visit } X - \text{Baseline Value}$$

**Relative change from baseline (%)** will be calculated as

$$\text{Relative Change from Baseline at Visit } X = \frac{\text{Value at Visit } X - \text{Baseline Value}}{\text{Baseline Value}} \times 100$$

Note: Subjects with a baseline value of '0' will be excluded from the calculation of relative change.

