## 5.6 Efficacy Analysis

Efficacy will be assessed by evaluation of the following variables:

- Epworth Sleepiness Scale (ESS) score change from baseline at the end of each treatment period
- ESS score responder rate at the end of each treatment period
- Absence of residual somnolence at the end of each treatment period
- Psychomotor Vigilance Test (PVT) variable change from baseline at the end of each treatment period
- Montreal Cognitive Assessment (MoCA) score change from baseline at the end of each treatment period
- Actimetry change from baseline at the end of each treatment period
- Number and duration of diurnal involuntary sleep attacks (subject diaries) change from baseline at the end of each treatment period
- Episodes of somnolence (subject diaries) change from baseline at the end of each treatment period

The Full Analysis set as well as the Per Protocol set will be used for the analysis of efficacy data.

**Treatment periods** will be considered as evaluable for efficacy analysis only if the following rules are satisfied:

- IMP is taken for at least 7 days during the treatment period
- Last IMP intake is at most 3 days before the corresponding end-of-treatment visit, i.e. a maximum of 3 IMP intakes can be missed leading up to the end-of-treatment visit.

**Washout periods** will be considered as evaluable for efficacy analysis only if the preceding treatment period is evaluable and the last IMP intake is 6 or more days before the corresponding end-of-washout visit.

For the purposes of these rules, EDVs are considered as end-of-treatment (if the preceding scheduled visit was VR/V1C/V2C) or end-of-washout (if the preceding scheduled visit was V1B/V2B) visits.

A trial period not being evaluable for efficacy analysis according to these rules is considered a major protocol deviation.

Efficacy analyses for the FAS will be performed using data available from all scheduled visits, as well as EDV visits satisfying the above criteria. Efficacy analyses for the PP will be performed using only data from trial periods unaffected by major protocol deviations.

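### SAP 4.6 applies efficacy-evaluability limits to early discontinuation visits in all analyses, so some safety values taken at these visits have no stated treatment assignment

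*SAP*

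**What the plan says.** - **SAP 4.6, treatment periods.** Treatment periods are defined as "The periods from the day after visits VR, V1C, and V2C, to the dates of visits V1B, V2B, and V3B respectively". The EDV rule follows: "If an early discontinuation visit (EDV) occurs after 7 or more IMP intakes, and not more than 3 days after the last IMP intake". When that holds, values from the visit are placed at the end of the ongoing treatment period. The rule is stated for statistical analyses in general, not for efficacy alone.
- **SAP 4.6, washout periods.** A second EDV rule places the visit at the end of the ongoing washout if it falls 6 or more days after the last intake. Washout values are summarised under the treatment just given. Washout is defined as starting the day after V1B or V2B.
- **SAP 4.8.** "Data collected at the EDV visit will be assigned to treatment periods according to the rules in Section 4.6". For safety, as treated: "Data will be assigned to treatments based on the treatment actually received during the corresponding treatment period".
- **SAP 4.4.** "The values collected at the EDV will be slotted according to date of EDV occurrence (see Section 4.6". Table 5 in that section gives the EDV its own visit number and output label.
- **SAP 5.6.** Treatment periods "will be considered as evaluable for efficacy analysis only if the following rules are satisfied". The first rule is "IMP is taken for at least 7 days during the treatment period"; the second allows at most 3 days between the last intake and the end-of-treatment visit.
- **SAP 4.7.** The endpoint value is "the last non-missing value collected during any end-of-treatment visit (V1B, V2B, or V3B"; the EDV is not named.
- **SAP 5.5.2 to 5.5.8.** Each section collects its safety data at V3B/EDV, among other visits, and tabulates by treatment. None has an EDV assignment rule of its own.
- **Protocol 4.4.2.** As far as possible, every subject who took IMP and does not complete has all the V3B examinations at an EDV.

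**The concern.** The 7-intake and 3-day limits make sense for efficacy: an ESS score after two days of drug, or several days off it, says little about a 14-day effect. Safety is different. A subject enters the Safety Set after one intake, and an early stop may itself reflect poor tolerability, since adverse events are a listed reason for withdrawal. SAP 5.1.2 describes the rules from the blind data review as bearing on efficacy and pharmacokinetic analysis, and nowhere gives a safety reason for them.

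Comparing the safety of each dose with placebo is the primary objective. Between first dose and the end-of-treatment visit the only scheduled contact is a phone call (protocol 6.1.4). For a subject who stops mid-period, the EDV is therefore normally the only laboratory, vital-signs and ECG assessment on that treatment. The protocol requires it to be collected, but the SAP does not say under which treatment it is summarised.

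**Working it through.** **1. Which EDVs meet a rule.** Let k be the number of intakes in the period before stopping and g the days from last intake to EDV, for a subject who has not attended that period's end-of-treatment visit.

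- Treatment rule (4.6): k ≥ 7 and g ≤ 3.
- Washout rule (4.6), read generously as covering any such subject: g ≥ 6.

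Take k = 1 to 14 at one intake a day and g = 0 to 7, which gives 14 × 8 = 112 combinations. Those meeting neither rule are:

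- k = 1–6 with g = 0–5: 6 × 6 = 36
- k = 7–14 with g = 4–5: 8 × 2 = 16
- total: 36 + 16 = 52 of 112

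If the washout rule does not reach a subject who stopped on treatment, the count is 6 × 8 + 8 × 4 = 80 of 112. These are counts of cases, not probabilities. With the EDV on the day of the last intake, the cases left open are exactly k = 1–6.

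**2. Whether another section fills the gap.**

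- SAP 4.4 slots the EDV by date but points back to 4.6.
- SAP 5.6 classes an EDV by the preceding scheduled visit, but only for its own efficacy rules.
- The as-treated sentence in 4.8 points to the treatment received. It sits beside the sentence routing EDV data through 4.6 and does not override it.

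**3. Effect on the tables.**

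- The laboratory and vital-signs shift tables run from baseline to endpoint. Since 4.7 names only V1B, V2B and V3B, such a subject would fall in the missing category for that treatment.
- MDS-UPDRS and QUIP-RS are summarised only at baseline and at the end of each treatment period, so an EDV not assigned to a period end has no place there.
- Laboratory, vital-signs, ECG, C-SSRS and physical-examination tables are by visit. Whether they have an EDV row, and under which treatment, is not stated in the SAP text.

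**4. How many subjects.** The plan gives no figure for EDVs. It randomises 60 to obtain 54 (54 / 0.90 = 60, an allowance of 6). Protocol 4.1 describes the 54 as completing as per protocol, so some of the 6 may finish with deviations and have no EDV.

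Assume stops are spread evenly over intakes 1–13. The share below 7 intakes is then 6/13 = 0.4615. With m EDVs, and a share p of stops falling inside a treatment period, the expected number affected is m × p × 0.4615:

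| m | p = 0.50 | p = 0.75 | p = 1.00 |
|---|---|---|---|
| 6 | 1.38 | 2.08 | 2.77 |
| 3 | 0.69 | 1.04 | 1.38 |

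This uses the intake limit alone and counts intakes within the period. SAP 4.6, unlike 5.6, does not say that the count is within the period. If it were cumulative over the trial, only period I stops (taken as one third) would be caught by the intake limit, and m = 6 would give 0.46 to 0.92.

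**The case against.** The strongest reply is that SAP 4.6 itself speaks of an ongoing treatment period at the time of an EDV, and that the follow-up period starts the day after V3B or the EDV. A period therefore exists for a subject who never reaches V1B, V2B or V3B, and the as-treated sentence in 4.8 could supply the treatment. The 7-intake and 3-day limits would then decide only whether the value counts as an end-of-period value. This carries weight. A reader might infer from the 4.6 definition that an early stopper has no treatment period at all; the documents do not support that. It conflicts with 4.6's own wording, and it would leave adverse events without a treatment, although 5.5.1 assigns them by the period containing onset. What remains is that 4.8 expressly routes EDV data through 4.6, and 4.6 does not say what happens when neither rule is met.

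A reader might also infer that every EDV more than 3 days after the last intake is unassigned. That goes too far: the washout rule may cover 6 days or more. Its reach is unclear for a subject who stopped on treatment, because washout is defined as starting after V1B or V2B. With 7 or more intakes, only days 4–5 are clearly open. Nor do the documents support a figure for late EDVs, as they state neither a maximum delay nor an expected share.

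Three further points stand. Table 5 gives the EDV its own label, and the table shells were not available, so an EDV row may already exist. The safety analysis is descriptive, with no test or decision rule. And keeping very short exposures out of 14-day summaries is defensible, provided the values appear somewhere under the right treatment.

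**Conclusion.** The gap is real but narrow. Limits that SAP 5.6 presents as efficacy criteria also govern safety through 4.6 and 4.8. Visit-based safety values from an EDV within 5 days of the last intake after 1–6 intakes, or 4–5 days after it with 7 or more, have no stated treatment assignment. The laboratory and vital-signs shift tables would show such subjects as missing.

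About 1–3 of 60 subjects would be affected, assuming 6 EDVs, even stopping over intakes 1–13 and half to all stops inside a treatment period. The possible range is 0–6, taking 6 as the upper limit on EDVs.

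It should not be read as a loss of safety data. All EDV values stay in the listings and adverse events are assigned by onset. Clinically significant laboratory changes are also recorded as adverse events, with the exceptions in protocol 6.3.2. Subjects who attend a scheduled end-of-treatment visit are unaffected for that treatment. What is at stake is the by-treatment summary of a few early stoppers' measurements, in a trial whose primary objective is safety by dose.

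**What to change.** - In SAP 4.6, limit the 7-intake and 3-day thresholds to efficacy, and state that intakes are counted within the treatment period.
- For safety outputs, assign EDV values to the treatment last received, as treated, whatever the number of intakes. Show them as an EDV row or flag with intakes taken and days since last intake.
- In SAP 4.7, define the endpoint for the safety shift tables per treatment period and include the EDV.

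Under this rule all 52 open combinations have an assignment. The efficacy analysis and its power are unchanged. The cost is SAP wording plus one EDV row or flag with two derived variables; no new data are needed. The downside is that a few short-exposure or drug-free values enter the safety summaries, where the flag keeps them distinguishable from 14-day values.
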